7.6. Efficacy Analyses

The following analyses will be based on the FAS using the IXRS randomization stratification factors, unless otherwise specified. The efficacy analyses will include all data from the Double-blind Period. For subjects who discontinue treatment or become unblinded prior to completion of the 48-week Double-blind Period, their efficacy data prior to start of the OLE Period will be included in this evaluation based on the ITT principle.

7.6.1. Primary Endpoint

The primary endpoint is the transfusion reduction response (TRR), defined as a \geq 50% reduction in transfused RBC units with a reduction of \geq 2 units of transfused RBCs in any consecutive 12-week period through Week 48 compared with the baseline transfusion burden (defined in Section 6.3.4.1) standardized to 12 weeks.

- Baseline transfusion burden standardized to 12 weeks (units/12-weeks) = total number of RBC units transfused during the 24-week period before the 'reference date'×12/24
- Reduction from baseline in transfusion burden for a 12-week period = Baseline transfusion burden standardized to 12 weeks Number of transfused RBC units in the 12-week period
- Percent reduction from baseline in transfusion burden for a 12-week period =100×(Baseline transfusion burden standardized to 12 weeks Number of transfused RBC units in the 12-week period)/ Baseline transfusion burden standardized to 12 weeks

Subjects who are withdrawn from the study before Week 12 (Day 85) will be considered nonresponders. A subject will meet the primary endpoint if, in any 12-week (84 days) consecutive period from the date of first dose in the Double-blind Period (Day 1) through Week 48 in the Double-blind Period both conditions below are met:

- Reduction from baseline in transfusion burden ≥ 2 RBC units
- Percent reduction from baseline in transfusion burden is $\geq 50\%$

The consecutive 12-week periods for the evaluation are Day 1 through Day 84, Day 2 through Day 85, and so on to cover all 84-day periods through Week 48 in the Double-blind Period.

7.6.1.1. Primary Analyses

The primary endpoint of TRR will be tested using the Mantel-Haenszel stratum weighted method adjusting for randomization stratification factors. The proportion of subjects who achieved a TRR will be summarized for each treatment arm. The adjusted difference in TRR rate between the mitapivat arm and placebo arm, along with the 95% CI and the 2-sided p-value, will be provided.

7.6.1.2. Sensitivity Analyses

The following sensitivity analyses will be performed:

- TRR will be analyzed using the methodology described for the primary analysis but based on PPS.
- TRR will be analyzed using the methodology described for the primary analysis but including only those subjects who completed 48 weeks of study treatment and who did not receive any concomitant medications (prior to completion of 48 weeks of study treatment) that could affect Hb concentrations. The list of associated concomitant medications will be finalized prior to the database lock and unblinding of the study for the primary analysis
- TRR will be analyzed using the methodology described for the primary analysis with the following changes: if a subject's Hb concentration met the individual transfusion threshold but the subject did not receive an RBC transfusion for a reason other than not clinically indicated then the transfusion will be considered missing; in this sensitivity analysis such subjects will be considered as having received an RBC transfusion on the day that the Hb concentration met the individual transfusion threshold, and the number of RBC units will be imputed as the number of RBC units received at the last transfusion before the Hb assessment associated with the missed transfusion

7.6.2. Key Secondary Endpoints

The key secondary endpoints are

• TRR2, defined as ≥50% reduction in transfused RBC units in any consecutive 24-week period through Week 48 compared with the 24-week baseline transfusion burden (defined in Section 6.3.4.1). The consecutive 24-week

periods for the evaluation are Day 1 through Day 168, Day 2 through Day 169, and so on to cover all 168-day periods through Week 48 in the Double-blind Period.

- TRR3, defined as ≥33% reduction in transfused RBC units from Week 13 through Week 48 compared with the baseline transfusion burden standardized to 36 weeks.
- TRR4, defined as ≥50% reduction in transfused RBC units from Week 13 through Week 48 compared with the baseline transfusion burden standardized to 36 weeks.

Baseline transfusion burden standardized to 36 weeks (units/36-weeks) = 24-week baseline transfusion burden (defined in Section 6.3.4.1)×36/24

Transfusion burden from Week 13 through Week 48 standardized to 36 weeks (units/36 weeks) = Number of transfused RBC units from Day 85 through Week 48 in the Double-blind Period \times 36/(Number of days from Day 85 through Week 48 in the Double-blind Period/7)

Percent reduction from baseline =100×(Baseline transfusion burden standardized to 36 weeks – Transfusion burden from Week 13 through Week 48 standardized to 36 weeks)/ Baseline transfusion burden standardized to 36 weeks

These endpoints (TRR2, TRR3, and TRR4) will be tested using the Mantel-Haenszel stratum weighted method adjusting for randomization stratification factors. The response rate based on the different definitions of response will be summarized for each treatment arm. The adjusted differences in response rate between the mitapivat arm and placebo arm, along with the 95% CI and the 2-sided p-value, will be provided.

Subjects who are withdrawn from the study before Week 24 (Day 169) will be considered nonresponders in TRR2. Subjects who are withdrawn from the study before Week 48 will be considered nonresponders in TRR3 and TRR4.

The following sensitivity analyses will be performed for each of these endpoints:

- TRR2, TRR3, TRR4 will be analyzed using the methodology described for the primary analysis but based on PPS.
- TRR2, TRR3, TRR4 will be analyzed using the methodology described for the primary analysis but including only those subjects who completed 48 weeks of study treatment and who did not receive any concomitant medications (prior to completion of 48 weeks of study treatment) that could affect Hb concentrations. The list of associated concomitant medications will be finalized prior to the database lock and unblinding of the study for the primary analysis
- TRR2, TRR3, TRR4 will be analyzed using the methodology described for the primary analysis with the following changes: if a subject's Hb concentration met the individual transfusion threshold but the subject did not receive an RBC transfusion for a reason other than not clinically indicated then the transfusion will be considered missing; in this sensitivity analysis such subjects will be

considered as having received an RBC transfusion on the day that the Hb concentration met the individual transfusion threshold, and the number of RBC units will be imputed as the number of RBC units received at the last transfusion before the Hb assessment associated with the missed transfusion

7.6.3. Additional Secondary Efficacy Endpoints

7.6.3.1. Additional Measures of Transfusion Burden

Change from Baseline in Transfused RBC Units from Week 13 Through Week 48

The change from baseline in transfused RBC units from Week 13 through Week 48 is derived as for the TRR3 and TRR4 endpoints, namely

- Baseline transfusion burden standardized to 36 weeks (units/36-weeks) = 24-week baseline transfusion burden (defined in Section 6.3.4.1)×36/24
- Transfusion burden from Week 13 through Week 48 standardized to 36 weeks (units/36 weeks) = Number of transfused RBC units from Day 85 through Week 48 in the Double-blind Period ×36/(Number of days from Day 85 through Week 48 in the Double-blind Period/7)
- Percent reduction from baseline =100×(Baseline transfusion burden standardized to 36 weeks Transfusion burden from Week 13 through Week 48 standardized to 36 weeks)/ Baseline transfusion burden standardized to 36 weeks
- Reduction from baseline = Baseline transfusion burden standardized to 36 weeks – Transfusion burden from Week 13 through Week 48 standardized to 36 weeks

and will be summarized by treatment arm.

Reduction (%) in RBC transfusion burden from Week 13 to Week 48 from the baseline transfusion burden standardized to 36 weeks will be analyzed using an analysis of covariance (ANCOVA) with treatment arm as the independent variable, and covariates for randomization stratification factors and baseline transfusion burden standardized to 36 weeks. Treatment effect will be evaluated as a contrast of mitapivat versus placebo. The least square (LS) means will be presented by treatment arm and the LS mean for the treatment difference between mitapivat and placebo will be presented with the associated 95% CI.

The frequency of subjects within the following percentage reduction categories will also be provided: <0, 0 to <20, 20 to <33, 33 to <50, \geq 33, and \geq 50%.

Transfusion Independence

Transfusion independence is defined as transfusion-free for ≥ 8 consecutive weeks through Week 48 in the Double-blind Period. The frequency of subjects achieving transfusion independence will be summarized by treatment arm. The adjusted difference in the proportion of subjects who achieve transfusion independence between the mitapivat arm and the placebo arm using a Mantel-Haenszel stratum weighted method adjusting for randomization stratification factors, along with the 95% CI, will be provided. For subjects who achieved transfusion independence, the duration of transfusion independence will be calculated as the number of days in the longest transfusion-free period starting on or after the 'reference date' (as defined in Section 6.3.4.1) through Week 48 in the Double-blind Period (evaluation period). Each transfusion-free period will be derived as follows:

- A transfusion-free period starts on the day after an RBC transfusion and ends the day before the next RBC transfusion
- For subjects who do not receive any RBC transfusions during the evaluation period, the start of the transfusion-free period is the 'reference date'
- For subjects who either do not receive any RBC transfusions during the evaluation period or receive an RBC transfusion during the evaluation period with no subsequent RBC transfusions during the evaluation period, the end of the transfusion-free period is censored at the end of the evaluation period

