8.7. Red Blood Cell Transfusions and Transfusion Modifications

The first dose of study drug must be administered within 7 days after Transfusion 0. Transfusion 0 is defined as the last RBC transfusion that was administered before randomization. Randomization must not occur until T0 has been completed.

All blood samples must be collected before administration of the study drug and before an RBC transfusion, including Transfusion 0, if an RBC transfusion is scheduled on the same day.

Transfusion history will be recorded for the 24-week period before randomization. Transfusion history includes T0. On-treatment transfusions will also be recorded. The transfusion history and on-treatment transfusion record includes transfusion dates, number of RBC units transfused, and pretransfusion Hb concentration. An RBC unit refers to packed red blood cell (pRBC) preparations. Due to hematocrit concentration differences in blood products used per local standards of care, 2 units of whole blood are equivalent to 1 unit of pRBCs and constitute an RBC unit. If available, the volume and the hematocrit of each transfused RBC unit should also be recorded. All RBC transfusions, including those received outside of the clinical study center, must be recorded.

A pretransfusion Hb threshold will be determined for each subject based on transfusion history. The pretransfusion Hb threshold is defined as the mean of all documented pretransfusion Hb concentration values recorded for the RBC transfusions administered during the 24-week transfusion history.

During the study, Investigators will monitor changes in Hb concentration and modify the subject's RBC transfusion schedule according to the guidelines in Table 10. Study drug dose modification guidance for excessive Hb response is provided in Section 6.7.1.1.

Subjects may receive RBC transfusions at the discretion of the Investigator for acute symptoms related to anemia or other comorbidities requiring immediate treatment (eg, infection or cardiopulmonary compromise).

Pretransfusion Hb Concentration ¹	RBC Transfusion Modification	
Hb concentration ≥ 1 g/dL above the pretransfusion Hb threshold and \leq ULN (by sex)	Delay RBC transfusion or decrease the number of RBC units to be transfused.	
>ULN (by sex)	Delay RBC transfusion.	
	• Recheck Hb concentration within 28 days.	
	• If Hb concentration remains >ULN (by sex) for ≥4 weeks, in the absence of RBC transfusions, modify the study drug dose as described in Section 6.7.1.1.	

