6.3.3. Study Day

The study day for assessments or events occurring on or after the start of study treatment (eg, AE onset, disease assessment) will be calculated as:

Study day=Date of the assessment or event-start of study treatment+1.

The study day for assessments or events occurring before the start of study treatment (eg, baseline characteristics, medical history) will be negative and calculated as:

Study day=Date of the assessment or event-start of study treatment.

There is no study day 0. The study day will be displayed in data listings.

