6.3.4. Baseline

6.3.4.1. Double-blind Period

Throughout the SAP for analyses based on the Double-blind Period, 'reference date' will be used to refer to randomization date for subjects randomized and not dosed, or the start of study treatment for subjects randomized and dosed.

Efficacy Evaluations

The 24-week baseline transfusion burden is defined as the total number of RBC units transfused during the 24-week period (168 days) before the 'reference date'. Baseline transfusion burden will be standardized to match the postbaseline assessment duration specified for each endpoint associated with reduction of transfusion burden from baseline.

For iron metabolism (Section 7.6.3.2),

baseline is defined as the last assessment before Transfusion 0 (the last RBC transfusion that is administered before randomization) to minimize the impact of transfusion on these endpoints. Baseline will be derived based on central laboratory data; if no central laboratory data are available, then local laboratory data will be used to derive the baseline.

Demographic and Other Baseline Characteristics

For summaries of demographic and other baseline characteristics based on the FAS, baseline is defined as the last assessment before the 'reference date'.

Safety Evaluations

For clinical laboratory assessments the following applies:

• Before deriving the baseline:

- If there are multiple records with the same assessment day and time from the same laboratory, the average value will be used.
- If there are multiple records with the same assessment day and time from different laboratories, the value from the central laboratory will be used.
- The baseline will then be the last value before the start of study treatment.

For all other safety parameters, the last assessment before the start of study treatment will be used as the baseline.

PD Evaluations

The baseline is defined as the pre-dose whole blood concentration of 2,3-DPG and ATP on study day 1. If this concentration is <LLQ, baseline will be set to missing.

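### When T0 falls two or more days before the reference date, the rule for duration of transfusion independence drops the interval before the first on-study transfusion, so an achiever can be reported below 8 weeks

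*SAP*

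**What the plan says.** SAP 7.6.3.1 defines transfusion independence as at least 8 consecutive transfusion-free weeks through Week 48. It sets no condition on when that run must begin.

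Duration is then derived for achievers only ("For subjects who achieved transfusion independence, the duration of transfusion independence will be calculated"), and it is "calculated as the number of days in the longest transfusion-free period starting on or after the" reference date. Three bullets define the periods:

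- General rule: "A transfusion-free period starts on the day after an RBC transfusion and ends the day before the next RBC transfusion".
- Start exception: "For subjects who do not receive any RBC transfusions during the evaluation period, the start of the transfusion-free period is the" reference date.
- End rule, for subjects with no transfusion or with none after their last one: "the end of the transfusion-free period is censored at the end of the evaluation period".

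The reference date (SAP 6.3.4.1) is the "randomization date for subjects randomized and not dosed, or the start of study treatment for subjects randomized and dosed". On the timing of T0, the last transfusion before randomization, Protocol 8.7 says: "The first dose of study drug must be administered within 7 days after Transfusion 0". The schedule of assessments (Protocol 1.2) places T0 on Day -7 to -1. SAP 6.3.3 adds: "There is no study day 0".

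**The concern.** The start exception covers only subjects with no on-study transfusion. For everyone else the opening interval starts the day after T0. If that day precedes the reference date, the interval fails the condition on start dates and is removed whole; it is not shortened to its on-study part.

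Two consequences follow. First, duration is calculated only for subjects with a run of at least 56 days, yet the rule can give one of them a value below 56 and so contradict the status that put the subject in the summary. Second, the value depends on whether T0 fell on Day -1 or Day -2, which is a matter of scheduling and not of response. One late transfusion can also turn a long response into a short one on paper.

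**Working it through.** The documents state no figure for this duration, so there is nothing to reproduce. The check applies the rule literally.

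**Inputs**
- Reference date: Day 1 for a dosed subject (SAP 6.3.4.1), with no Day 0 (SAP 6.3.3).
- T0: Day -7 to -1 (Protocol 1.2).
- Threshold: 8 × 7 = 56 days (SAP 6.4.2 sets 1 week = 7 days).
- End of evaluation period: Day 48 × 7 = 336. This is an assumption, because SAP 7.6.3.1 does not give the day. Ending on Day 337 adds 1 to any value that comes from the last run.

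**Rule.** Let the on-study transfusions fall on Days t1 < t2 < ... < tk.
- The opening period runs from the day after T0 to Day t1 − 1 and is kept only if it starts on or after Day 1. Its on-study length is t1 − 1.
- A middle period has length t(i+1) − t(i) − 1.
- The last period has length 336 − tk.
- The reported duration is the longest period kept.

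**Where the switch falls.** T0 on Day -1 gives a start on Day 1, which is kept. T0 on Day -2 gives a start on Day -1, which is dropped, and the same holds back to Day -7. So six of the seven scheduled T0 days drop the opening interval.

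**Results (days)**

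| On-study transfusions | Opening run from Day 1 | Longest later run | Reported, T0 Day -1 | Reported, T0 Day -7 to -2 |
|---|---|---|---|---|
| Day 71, then every 21 days to Day 323 | 70 | 20 | 70 | 20 |
| Day 71, then every 28 days to Day 323 | 70 | 27 | 70 | 27 |
| Day 300 only | 299 | 336 − 300 = 36 | 299 | 36 |
| Day 281 only | 280 | 336 − 281 = 55 | 280 | 55 |
| Day 200 only | 199 | 336 − 200 = 136 | 199 | 136 |
| Day 100, then every 21 days to Day 268 | 99 | 336 − 268 = 68 | 99 | 68 |
| None | 336 | none | 336 | 336 |

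In the first two rows the last run is 336 − 323 = 13 days, so the spacing of the later transfusions sets the reported value.

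With a single transfusion on Day d and T0 on Day -2 or earlier, the reported value is 336 − d. It is below 56 for every d from 281 to 336.

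**General statement.** If the opening interval is the subject's only run of 56 days or more, every remaining run is at most 55 days, so the reported value must fall below 8 weeks. If a later run also reaches 56 days, the value stays at or above 56 but is understated whenever the opening run is the longest.

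**After the repair.** If the first period starts at the later of the reference date and the day after T0, the Day 71 pattern with 28-day spacing gives 70 and the Day 300 case gives 299 for every T0 from Day -7 to -1. The subject with no transfusion stays at 336.

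**The case against.** There are four arguments on the other side.

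- **Little depends on it.** Duration of transfusion independence is not listed as an endpoint in Protocol Table 3, Protocol 10.4.3.2 or SAP Table 2, and no test, interval or comparison between arms is attached to it. This stands, and it limits how much the point matters.
- **A programmer might cut the opening period at the reference date anyway.** The SAP names a window from the reference date through Week 48, and the third bullet clips at its end. But no sentence clips at its start for transfused subjects. The second bullet supplies a start only for those never transfused, and it would be unnecessary if clipping were general. Even on the charitable view, the text lets two careful programmers report 70 and 20 from the same record.
- **The three bullets may also be meant to derive responder status.** No achiever could then be reported below 56 days, but some subjects with a long opening run would stop being responders. The SAP does not say this, and the binary definition has no start condition. As written, the responder analysis is therefore unaffected. The link should still be stated.
- **The cases are constructed.** This is fair as to frequency: the documents give no distribution of T0 gaps or of times to first transfusion. They are nonetheless compatible with the protocol. Section 8.7 allows transfusion for acute symptoms or comorbidities, so an isolated late transfusion is possible.

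**Conclusion.** The concern holds. Read as written, the rule removes the opening interval for any subject who is transfused on study and whose T0 was on Day -2 or earlier. It can report an achiever at 20 days instead of 70, or 36 instead of 299. The day counts assume that the subject was dosed, that Day 1 is the reference date and that the evaluation period ends on Day 336.

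The effect is confined to a descriptive summary. The transfusion-independence proportion with its Mantel-Haenszel difference and interval, TRR, TRR2 to TRR4 and the alpha allocation do not change. How many subjects would be affected cannot be determined from the documents. The text should be corrected before unblinding, because a stated rule gives values that conflict with the group it describes.

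**What to change.** Add a bullet to SAP 7.6.3.1: for subjects with at least one RBC transfusion in the evaluation period, the first transfusion-free period runs from the reference date to the day before the first on-study transfusion. Wording the start as the later of the reference date and the day after T0 also covers a T0 that falls on the reference date itself.

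State too that responder status and duration come from this one set of periods. That settles a borderline case on which the SAP is silent: a run that reaches 56 days only by counting days before the reference date. For example, T0 on Day -7 and a first transfusion on Day 51 give 6 days before Day 1 plus 50 from Day 1, or 56.

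The cost is one bullet, one sentence and a small programming change. No new data are needed.

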7.6.3.2. Iron Metabolism

Iron metabolism will be assessed based on iron, serum ferritin, total iron binding capacity, and transferrin saturation.

Values and changes from baseline will be summarized based on descriptive statistics, by treatment arm and study visit, through Week 48 of the Double-blind Period. Change from baseline will be compared between treatment arms following the same methodology as described in Section 7.6.3.1 for reduction from baseline in RBC transfusion burden.

By-subject longitudinal plots will be presented with values at baseline and postbaseline, transfusions, and prescribed dose over time. The plots will further include TRR status, treatment arm, age, sex, race, randomization stratification factors, 24-week baseline transfusion burden, and hydroxyurea status.

